**【Setting basis】**

- (1)(3)(5)-(7) were set because they may affect the evaluation of efficacy in this study.
- (2) was set since it is the same active ingredient as the investigational drug, it affects the evaluation of efficacy in this study and ensures safety
- (4) was set because there is a risk of enhancing or diminishing the action when used in combination with an investigational drug.

2. From the time of screening to the follow-up end, the following therapies are prohibited:

- (1) Obesity surgery (sleeve gastrectomy, gastric bypass surgery, sleeve bypass surgery, etc.)

**【Setting basis】**

- (1) was set because it is considered to affect the safety of the subjects and the efficacy evaluation of this study.

### 8.3.2 Continued use of pretreatment and combination therapy

When the following drugs and therapies are used in combination during the treatment period, they can be used under the conditions described.

1. Drugs restricted for concomitant use include:

- (1) Antihypertensive drug
- (2) Drugs to treat dyslipidemia
- (3) Drugs to treat diabetes treatment (DPP-4 inhibitor, SU preparation,  $\alpha$ -glucosidase inhibitor, metformin)

The above concomitant drugs may be used concomitantly only if the dose is kept constant from 12 weeks before screening and the drug is continuously used. The dose is not changed until the end of the investment drug administration.

\* Regarding antihypertensive drugs, if symptoms worsen, additional administration of only calcium antagonists is possible.

\* Regarding diabetes treatment drugs, if the symptoms worsen, the dose can be gradually reduced.

The use of drugs for concomitant use after the end of the administration of the investigational drug is not restricted.

**【Setting basis】**

The above therapeutic agents are reportedly efficacious in patients with NAFLD/NASH. However, from the viewpoint of subject safety, it is difficult to designate these drugs as a concomitantly prohibited drug. Therefore, it was judged that there would be no problem in evaluating safety and efficacy if the subjects had stable pathological conditions with no change in dose from 12 weeks before screening and no change in dose during the study period.

2. Treatments restricted for concomitant use

Not applicable

## 8.4 Guidance to subjects

clinical trial protocol 番号 : YCU-21001

#### 8.4.1 Medication guidance and compliance items

The principal investigator, sub-investigator, or clinical trial collaborators will give medication guidance to the subjects, paying attention to the following points at the time of delivery of this investigational drug:

1. When to take, how many times to take, and how to take; the investigational drug should be taken after dinner on the day of V2, and the final administration should be the morning of V7, at 16 weeks.
2. At the time of visit, the subject was expected to fast for 8 hours before the examination.
  - If the clinic visit is in the morning, do not eat breakfast, take an investigational drug, and come to the hospital.
  - If the clinic visit is later in the afternoon, eat breakfast, take the investigational drug, do not eat lunch, and come to the hospital.
  - Breakfast should be skipped if necessary to comply with an 8-hour fast before the test.
3. If a dosing time was missed accidentally, bring any remaining medicine and an empty sheet of paper at the next visit.
4. If a dose is missed, take it at least 6 hours before the next dose.
5. If a subject is unsure about the medication, the subject should contact the principal investigator, sub-investigator, or clinical trial collaborators. The subject should be instructed to hand in their drug diary and fill in the medication status, daily status, etc.
6. While taking investigational drugs, subjects should be instructed to be careful when engaging in dangerous activities, such as work at heights and driving a car, and to minimize alcohol intake.

#### 8.4.2 Recovery of drugs that are not taken

The principal investigator, sub-investigator, or clinical trial collaborators should recover any unconsumed drug from the subject. The drug should be given to the investigational drug administrator. If the unconsumed drug cannot be recovered, the reason should be provided in the medical record.

### 8.5 Overall flow of this clinical trial

#### 8.5.1 Consent acquisition

The principal investigator or sub-investigator obtains written consent from the subject at the time of screening in accordance with “エラー! 参照元が見つかりません。 エラー! 参照元が見つかりません。” of this clinical trial protocol. After obtaining consent, the required items are completed in the "Subject Screening List".

#### 8.5.2 Observation, inspection, and survey items during screening (V1)

The principal investigator or sub-investigator confirms that the subject complies with the provisions of "エラー! 参照元が見つかりません。 エラー! 参照元が見つかりません。" of this clinical trial protocol and does not violate the provisions of "エラー! 参照元が見つかりません。 エラー! 参照元が見つかりません。". If the subject is receiving medical treatment from another doctor, contact that doctor about the subject's participation in the clinical trial and record the contact in the medical record.

- Selection criteria
- Subject background
- Serological test
- Chest X-ray
- Electro-cardiogram
- Physical examination
- Vital signs

clinical trial protocol 番号 : YCU-21001

- MRI \* (MRE, MRI-PDFF)
- Liver biopsy (information collection only for cases with data within 32 weeks before screening)
- Hematology/coagulation, urinalysis
- Endocrinological examination
- Biochemical test 1
- Biochemical test 2
- Combination drug

\*: Measurements will be carried out by a specialist, such as a principal investigator. Eligibility will be judged by the principal investigator. Measurements by a specialist should be performed by the end of the trial.

#### 8.5.3 Pre-administration observation, examination, survey items (V2)

- Selection criteria
- Physical examination
- Vital signs
- Subjective and objective symptoms
- Pregnancy test
- Hematology / coagulation \*, urinalysis \*
- Biochemical test 1 \*
- Biochemical test 2 \*
- Others
- Genetic testing
- Concomitant drug

\*If there is data within 4 weeks, it can be substituted.

#### 8.5.4 Two weeks after administration (V3)

- Vital signs
- Subjective and objective symptoms
- Medication status
- Concomitant drug
- Adverse events

#### 8.5.5 Observation, examination, survey items of 4 weeks (V4), 8 weeks (V5), and 12 weeks (V6) after administration

- Vital signs
- Subjective and objective symptoms
- Biochemical test 1
- Medication status
- Concomitant drug
- Adverse events

#### 8.5.6 Observation, examination, and survey items at 16 weeks of administration/termination (V7/end of trial [EOT])

- Physical examination
- Vital signs
- Subjective and objective symptoms
- Pregnancy test
- MRI \* (MRE, MRI-PDFF)

clinical trial protocol 番号 : YCU-21001

- Hematology/coagulation, urinalysis
- Biochemical test 1
- Biochemical test 2
- Others
- Medication status
- Concomitant drug
- Adverse events

\* Measure by a specialist, such as a principal investigator. Measurements by a specialist should be performed by the end of the trial.

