## 7.4.2 Labeling

For 4 mg/day

clinical trial protocol 番号 : YCU-21001

For clinical trial 4mg/day Allocation number:
 
WY-8678
 
Content: 14 tablets × 4 sheets × 5 bags  Storage method: Room temperature  Serial number: GK27  Expiration date: 2025.9
 
Yokohama City University Hospital, Department of Palliative  Medicine Clinical Instructor: [name]
 
[name]

---

For 8 mg/day

For clinical trial 8 mg/day Allocation number:
 
WY-8678
 
Content: 14 tablets × 8 sheets  Storage method: Room temperature  Serial number: GK27  Expiration date: 2025.9
 
Yokohama City University Hospital, Department of Palliative  Medicine Clinical Instructor: [name]
 
[name]

---

Fig. 7.4.2-1 Labeling of WY-8678

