## 8 Clinical trial design and clinical trial schedule

### 8.1 Clinical trial design

#### 8.1.1 Clinical trial method

Single-center, randomized

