## 9 Observation, inspection, evaluation items, and timing

### 9.1 Observation, inspection, and evaluation schedule list

The principal investigator or sub-investigator conducts observations, inspections, surveys, etc. according to the table below. If a blood sampling test is to be performed at the time of the subject's visit, the subject should fast for 8 hours before the blood is collected.

Table 9.1-1 Observation, examination, and evaluation schedule

		8-week	16-week						4-week
Screening		Group A: WY-8678 4 mg/day: one tablet per session, twice per day						Follow-up	
		Group B: WY-8678 8 mg/day: 2 tablets per session, twice per day							
Week	Consent acquisition	Screening	Treatment period						Follow-up
		V1	V2	V3	V4	V5	V6	V7/EOT	V8
		Within 8 weeks prior to registration	Prior to start of administration	2 weeks	4 weeks	8 weeks	12 weeks	16 weeks	4 weeks after end of administration
Tolerable range		-8 weeks	-	±3 days	±7 days	±7 days	±7 days	±7 days	±7 days
Consent acquisition	○								
Selection criteria		○	○						
Subject background		○							
Serological test a		○							
Chest X-ray		○							
Electro-cardiogram		○							
Physical examination b		○	○					○	
Vital signs c		○	○	○	○	○	○	○	○
Subjective and objective symptoms			○	○	○	○	○	○	○
Pregnancy test d			○					○	
MRI e		○						○	
Liver biopsy		△							
Randomization			○						
Hematology test / urine test f		○	○ i					○	○
Endocrinological examination		○							
Biochemical test 1		○	○ i		○	○	○	○	○
Biochemical test 2 g		○	○ i					○	
Other h			○					○	
Somatic cell genetic test			●						
Providing drugs			○		○	○	○		
Checking the medication status				○	○	○	○	○	
Survey of combination drugs		○	○	○	○	○	○	○	
Investigation of adverse events				○	○	○	○	○	○

○: Implemented

△: Information is collected for cases with liver biopsy results (within 32 weeks before screening).

●: Genetic testing is an essential test.

a: Contains HBs antigen, HCV antibody, and HCV-RNA.

b: Includes height (V1 only) and weight. BMI (V1) is calculated based on height and weight.

c: Vital signs include blood pressure, pulse rate, and axillary body temperature.

d: For women of childbearing potential, a urine pregnancy test will be performed on V2 and V7.

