e: Use MRI to measure MR elastography (MRE) and liver fat (PDFF). Patients terminating before V7 (week 16) should undergo MRI at the end of treatment if they have completed at least 4 weeks of treatment.

clinical trial protocol 番号 : YCU-21001

f-h: Refer to Table 9.1-2 Clinical laboratory items.  
i: If there is data within 4 weeks, it can be substituted.

Table 9.1-2 Clinical laboratory items

Biochemical test 1 (on an empty stomach) (Screening, every visit, follow-up, termination)	Biochemical test 2 (on an empty stomach) (At the time of screening, V2, V7, termination)	Others (V2, V7/at termination)
Albumin (Alb) ALT Alkaline phosphatase (ALP) Amylase AST Blood urea nitrogen (BUN) Chlorine (Cl) Creatinine (Cre) Estimated glomerular filtration rate (eGFR)  (during screening) $\gamma$ -GTP Lactate dehydrogenase (LDH) Potassium (K) Sodium (Na) Calcium (Ca) Total bilirubin (T-Bil) Total protein (TP) Uric acid	HDL-C LDL-C Non-HDL-C  TC TG  Glucose HbA1c Insulin HOMA-IR 	[Inflammation] High-sensitivity C-reactive protein (CRP) Ferritin TNF- $\alpha$ Interleukin-6 CK18 / M30 Endotoxin LBP Endotoxin activity [Endocrine] C-peptide Total GLP-1 / Active GLP1 Leptin Adiponectin [Fibrosis] hyaluronic acid PIIP TIMP-1 M2BPGi Type IV Collagen 7s ELF score3 Fibrosis-4 (FIB-4)  [Fat] Chylomicron cholesterol Chylomicron triglyceride Lipoprotein cholesterol LDL triglyceride VLDL cholesterol VLDL triglyceride Free cholesterol (F-cho) Apolipoprotein A1 Apolipoprotein B Adipsin Free fatty acid (FFA) [Others] TMAO
Hematological examination / coagulation (During screening, V2, V7, follow-up, termination)	Urinalysis (Screening, V2, V7, termination, follow-up)	
Hematocrit (Ht) Hemoglobin (Hb) Platelet count Number of red blood cells White blood cell count and white blood cell fraction (neutrophils, eosinophils, basophils, lymphocytes, monocytes) International Normalized Ratio (INR)	Latent blood Urine sugar pH Urine protein Specific gravity Urobilinogen  Pregnancy test  (At V2, V7, at termination)	
Somatic cell genetic test (V2)	Endocrinological examination (at the time of screening)	Serological test (at the time of screening)
PNPLA3 TM6SF2	Free thyroxine (FT4) Free triiodothyronine (FT3) Thyroid stimulating hormone	HBs antigen HCV antibody 

 Postmenopausal is defined as a condition without medical causes and no menstruation for more than 12 months.

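### The scans behind the primary endpoint are read without masking to visit, in a before/after test with no control; a masked, shuffled batch reading would guard against this at little cost

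*Protocol*

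**What the plan says.** Both scans that make up the primary endpoint fall under the same reading rule.

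- Screening (V1), Protocol 8.5.2: "Measurements will be carried out by a specialist, such as a principal investigator. Eligibility will be judged by the principal investigator". A further sentence asks for specialist measurement before the trial ends.
- Week 16 (V7/EOT), Protocol 8.5.6: "Measure by a specialist, such as a principal investigator. Measurements by a specialist should be performed by the end of the trial".

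Section 8.1.1 describes the design only as "Single-center, randomized". No placebo is described, and section 8.1.2 says efficacy is evaluated within each group, not by comparing groups. Section 13.1 makes the two doses together the main interest and tests the responder rate against 0.25. A responder is a subject whose PDFF falls by at least 3.46 points from baseline to week 16 (section 9.5). A screening PDFF of at least 8% is an inclusion criterion (section 4.2).

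The protocol does not ask for the reader to be masked to visit, for the scans to be read in random order, or for a particular V1 reading to serve as baseline.

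**The concern.** The primary result depends on the difference between two readings of the same liver. A reader who knows which scan is week 16 can, without intending to, read it lower or the screening scan higher. The protocol names an investigator as an acceptable reader and does nothing to withhold the visit.

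In a trial with a concurrent control, a shift of this kind would largely cancel between arms if the reader did not know the arm. Here the comparator is a constant, and both dose groups are pooled on the same side of the test. Any systematic difference between V1 and V7 readings therefore goes straight into the responder rate. The endpoint is also a hard cut at 3.46 points, so a small shift reclassifies subjects who lie near it. At stake is the proof-of-concept decision to go on to the next phase.

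**Working it through.** **Inputs from the protocol (13.1, 13.4.1).** N = 28 pooled; null responder rate 0.25; alternative 0.50; one-sided 5%; success if the lower limit of the 90% Clopper-Pearson interval exceeds 0.25. The direction of the hypothesis is taken from section 13.1, because section 13.4.1 prints it reversed.

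**Step 1: reproduce the plan's rule.** Let X ~ Binomial(28, θ).

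- Lower 90% Clopper-Pearson limit: 0.238 at 11/28 and 0.269 at 12/28. Success therefore needs X ≥ 12.
- P(X ≥ 12 | θ = 0.25) = 0.0294.
- P(X ≥ 12 | θ = 0.50) = 0.828.

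The stated sample size of 28 for 80% power is reproduced.

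**Step 2: misread subjects, with no assumption about SD.** If k true non-responders are read as responders, success needs only 12 − k true responders.

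- k = 1: P(X ≥ 11 | 0.25) = 0.068.
- k = 2: P(X ≥ 10 | 0.25) = 0.138.

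One misread subject takes the rule from 2.9% to above the planned 5%.

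**Step 3: a systematic reading shift.** The protocol gives no SD of change and no reader error, so the following are assumptions: the PDFF change is normal with SD s of 3 to 5 points, the true rate is exactly 0.25, and the reading difference is shifted by b points in the favourable direction. Then

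θ(b) = Φ(Φ⁻¹(0.25) + b/s) = Φ(−0.6745 + b/s),

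and the false-positive rate is P(X ≥ 12 | 28, θ(b)).

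| Shift b (points) | θ at SD 5 / 4 / 3 | False-positive rate at SD 5 / 4 / 3 |
|---|---|---|
| 0 | 0.250 | 2.9% |
| 0.1 | 0.256 / 0.258 / 0.261 | 3.5% / 3.7% / 4.0% |
| 0.25 | 0.266 / 0.270 / 0.277 | 4.6% / 5.2% / 6.1% |
| 0.5 | 0.283 / 0.291 / 0.306 | 7.0% / 8.5% / 11.6% |
| 1.0 | 0.318 / 0.336 / 0.366 | 14.5% / 19.8% / 30.9% |

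Because the binomial is discrete, the rule starts at 2.9%. That leaves room to absorb a shift of 0.1 point, and at the larger SD a shift of 0.25 point. From 0.5 point upward, the nominal 5% is exceeded at every SD in the range.

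**Step 4: size of the remedy.** 28 subjects × 2 scans = 56 reads. About 28 of these repeat a reading already made at screening. N and the 12/28 rule do not change.

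**The case against.** **The size of the bias is not established.** Section 9.5 calls PDFF stable and highly reproducible, and nothing in the protocol shows a shift of 0.5 point or more. This stands: the upper rows of the table show how sensitive the rule is and do not predict what this trial will do. Low random error, however, does not exclude a directional error by a reader who knows the visit.

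**The investigator is only an example of a reader.** Section 8.5.2 gives measurement to a specialist and the eligibility decision to the principal investigator: "Eligibility will be judged by the principal investigator". A reader might infer that the investigator's own V1 reading decides entry and then becomes the baseline. The text does not say so, and it can equally be read as an eligibility judgement followed by a later specialist measurement. What remains is that neither the masking nor the choice of baseline reading is stated.

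**Dose visibility adds little.** The daily dose is printed on the box ("For clinical trial 8 mg/day", section 7.4.2) and tablet counts differ by group. But the primary test pools the doses, and a box label does not show what the reader of the scan sees. The point rests on knowledge of the visit.

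**The 8-week screening window is a separate matter.** V1 may take place "Within 8 weeks prior to registration", while a footnote to the schedule in section 9.1 says "If there is data within 4 weeks, it can be substituted". A reader might infer that the baseline MRI breaks a 4-week rule. It does not: the footnote is attached to laboratory tests scheduled at V2, and no MRI is scheduled there. A 4-week MRI limit could also force repeat scans.

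**A false positive only leads to a controlled trial.** This is true and limits the harm, but that decision is the purpose of this study.

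**Conclusion.** The point holds as a cheap improvement that should be made. The protocol sets a reading rule for its only primary measurement without masking to visit, in a design where nothing cancels a directional reading difference. The decision is sensitive: one non-responder read as a responder takes the false-positive rate from 2.9% to 6.8%. The shift results (3.5-4.0% at 0.1 point up to 14.5-30.9% at 1 point) rest on an assumed normal change, an assumed SD of 3 to 5 points and an assumed direction.

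Two stronger readings are not supported. The protocol does not show that biased reading will occur. Nor would masked reading make the before/after comparison safe: it reduces expectation bias from knowing the visit, but leaves natural change, scan-level regression to the mean after selection at PDFF ≥ 8%, and scanner drift.

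**What to change.** State in sections 8.5.2 and 8.5.6 that:

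1. the planned specialist reads all V1 and V7 scans in one batch at trial end, with subject, date, visit and dose removed and the order shuffled;
2. these readings define baseline and week 16 for the primary endpoint;
3. the screening reading is used for eligibility only;
4. where possible, the batch reader is an already available specialist who did not make the screening reading.

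This fits the existing text, which already lets specialist measurement take place up to the end of the trial. The cost is de-identifying, shuffling and reading about 56 scans, about half of them repeat reads of screening scans. No extra scan or patient is needed, and the sample size and decision rule stay as they are. The MRI window needs no change on this account.

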#### 8.5.7 Observation, examination, and survey items 4 weeks after the end of administration (follow-up, V8)

- Vital signs
- Subjective and objective symptoms
- Biochemical test 1
- Hematology/coagulation, urinalysis
- Adverse events

clinical trial protocol 番号 : YCU-21001

## 9 Observation, inspection, evaluation items, and timing

### 9.1 Observation, inspection, and evaluation schedule list

The principal investigator or sub-investigator conducts observations, inspections, surveys, etc. according to the table below. If a blood sampling test is to be performed at the time of the subject's visit, the subject should fast for 8 hours before the blood is collected.

Table 9.1-1 Observation, examination, and evaluation schedule

		8-week	16-week						4-week
Screening		Group A: WY-8678 4 mg/day: one tablet per session, twice per day						Follow-up	
		Group B: WY-8678 8 mg/day: 2 tablets per session, twice per day							
Week	Consent acquisition	Screening	Treatment period						Follow-up
		V1	V2	V3	V4	V5	V6	V7/EOT	V8
		Within 8 weeks prior to registration	Prior to start of administration	2 weeks	4 weeks	8 weeks	12 weeks	16 weeks	4 weeks after end of administration
Tolerable range		-8 weeks	-	±3 days	±7 days	±7 days	±7 days	±7 days	±7 days
Consent acquisition	○								
Selection criteria		○	○						
Subject background		○							
Serological test a		○							
Chest X-ray		○							
Electro-cardiogram		○							
Physical examination b		○	○					○	
Vital signs c		○	○	○	○	○	○	○	○
Subjective and objective symptoms			○	○	○	○	○	○	○
Pregnancy test d			○					○	
MRI e		○						○	
Liver biopsy		△							
Randomization			○						
Hematology test / urine test f		○	○ i					○	○
Endocrinological examination		○							
Biochemical test 1		○	○ i		○	○	○	○	○
Biochemical test 2 g		○	○ i					○	
Other h			○					○	
Somatic cell genetic test			●						
Providing drugs			○		○	○	○		
Checking the medication status				○	○	○	○	○	
Survey of combination drugs		○	○	○	○	○	○	○	
Investigation of adverse events				○	○	○	○	○	○

○: Implemented

△: Information is collected for cases with liver biopsy results (within 32 weeks before screening).

●: Genetic testing is an essential test.

a: Contains HBs antigen, HCV antibody, and HCV-RNA.

b: Includes height (V1 only) and weight. BMI (V1) is calculated based on height and weight.

c: Vital signs include blood pressure, pulse rate, and axillary body temperature.

d: For women of childbearing potential, a urine pregnancy test will be performed on V2 and V7.

e: Use MRI to measure MR elastography (MRE) and liver fat (PDFF). Patients terminating before V7 (week 16) should undergo MRI at the end of treatment if they have completed at least 4 weeks of treatment.

clinical trial protocol 番号 : YCU-21001

f-h: Refer to Table 9.1-2 Clinical laboratory items.  
i: If there is data within 4 weeks, it can be substituted.

Table 9.1-2 Clinical laboratory items

Biochemical test 1 (on an empty stomach) (Screening, every visit, follow-up, termination)	Biochemical test 2 (on an empty stomach) (At the time of screening, V2, V7, termination)	Others (V2, V7/at termination)
Albumin (Alb) ALT Alkaline phosphatase (ALP) Amylase AST Blood urea nitrogen (BUN) Chlorine (Cl) Creatinine (Cre) Estimated glomerular filtration rate (eGFR)  (during screening) $\gamma$ -GTP Lactate dehydrogenase (LDH) Potassium (K) Sodium (Na) Calcium (Ca) Total bilirubin (T-Bil) Total protein (TP) Uric acid	HDL-C LDL-C Non-HDL-C  TC TG  Glucose HbA1c Insulin HOMA-IR 	[Inflammation] High-sensitivity C-reactive protein (CRP) Ferritin TNF- $\alpha$ Interleukin-6 CK18 / M30 Endotoxin LBP Endotoxin activity [Endocrine] C-peptide Total GLP-1 / Active GLP1 Leptin Adiponectin [Fibrosis] hyaluronic acid PIIP TIMP-1 M2BPGi Type IV Collagen 7s ELF score3 Fibrosis-4 (FIB-4)  [Fat] Chylomicron cholesterol Chylomicron triglyceride Lipoprotein cholesterol LDL triglyceride VLDL cholesterol VLDL triglyceride Free cholesterol (F-cho) Apolipoprotein A1 Apolipoprotein B Adipsin Free fatty acid (FFA) [Others] TMAO
Hematological examination / coagulation (During screening, V2, V7, follow-up, termination)	Urinalysis (Screening, V2, V7, termination, follow-up)	
Hematocrit (Ht) Hemoglobin (Hb) Platelet count Number of red blood cells White blood cell count and white blood cell fraction (neutrophils, eosinophils, basophils, lymphocytes, monocytes) International Normalized Ratio (INR)	Latent blood Urine sugar pH Urine protein Specific gravity Urobilinogen  Pregnancy test  (At V2, V7, at termination)	
Somatic cell genetic test (V2)	Endocrinological examination (at the time of screening)	Serological test (at the time of screening)
PNPLA3 TM6SF2	Free thyroxine (FT4) Free triiodothyronine (FT3) Thyroid stimulating hormone	HBs antigen HCV antibody 

 Postmenopausal is defined as a condition without medical causes and no menstruation for more than 12 months.

 Perform HCV-RNA test if HCV antibody is positive or if hepatitis C is present in the past.

 According to the calculation formula.

